4.4. Benefit/Risk Assessment

[figure not shown]
Nonclinical studies and the completed Phase 1 study have all provided safety information that support plasma concentrations and exposures up to those associated with the 5 mg/kg SC weekly dose level. Given the population of subjects who have failed to achieve an adequate response to existing biological products, PK, and safety data from the Phase 1 first-in-human study (KPL-404-C101), and nonclinical data, the Sponsor believes that KPL-404 has the potential to improve outcomes in this study population, with low risk of significant adverse events.

5. STUDY OBJECTIVES AND ENDPOINTS

See Section 10 and Section 11.4 for detailed explanations of assessments and efficacy endpoints, respectively.

Primary Objectives:	Primary Endpoints:	
Cohorts 1 and 2: To evaluate the dose- response relationship as measured by safety, tolerability, and pharmacokinetics of multiple subcutaneous (SC) doses of KPL-404 versus placebo.	Cohorts 1 and 2: Incidence of treatment-emergent adverse events (TEAEs) Maximum serum concentration (C _{max}) Area under the serum concentration time curve from 0 to the end of the dosing interval (AUC _{0-t})	
• Cohorts 3 and 4: To evaluate the efficacy of KPL-404 versus placebo for the treatment of rheumatoid arthritis (RA).	Cohorts 3and 4: Change from baseline in disease activity score of 28 joints using C- reactive protein (DAS28-CRP) at Week 12	
Secondary Objectives:	Secondary Endpoints:	
Cohorts 1 and 2: To evaluate the efficacy of multiple SC doses of KPL-404 versus placebo for the treatment of RA.	Cohorts 1 and 2: Change from baseline in DAS28-CRP at Week 12	
Cohorts 3 and 4: To evaluate the safety, tolerability, and pharmacokinetics (PK) of KPL-404 versus placebo.	Cohorts 3 and 4: Incidence of TEAEs C _{max} AUC _{0-t}	
Other Objective:	Other Endpoints (All Cohorts):	
• To		
	Proportion of subjects achieving ACR20 responses at Week 12	

6. INVESTIGATIONAL PLAN

6.1. Overall Study Design

Figure 2 displays the overall schema for the study. A detailed outline of procedures and activities is provided in Appendix 1.

This is a 28-week (up to 4-week screening period, 12-week treatment period, and 12-week safety follow-up period), multicenter, randomized, double-blind, placebo-controlled, multiple dose proof-of-concept study with PK lead-in designed to assess the safety, PK, efficacy, and PD of KPL-404 in subjects with moderate to severe, active RA who have inadequate response to or are intolerant to at least one biologic disease-modifying anti-rheumatic drug (bDMARD) or JAKi. The objectives of the study are to evaluate safety, efficacy, and PD of KPL-404 compared with placebo across the estimated therapeutic range and to characterize PK across varying dose levels of KPL-404.

After signing the informed consent form (ICF), subjects will enter the screening period (Day -28 to -1), before returning for the baseline visit and administration of the first dose (Day 1). Subjects can be rescreened only once, at the discretion of the Investigator and with approval from the medical monitor. Abnormal laboratory values may in certain cases be repeated with the approval of the medical monitor without the need for rescreening. If a subject is rescreened, a new subject number will be provided, and laboratory assessments can be repeated once where appropriate.

All randomized subjects will receive a SC injection of the investigational product (IP) on Day 1 at the study site. In the first 2 cohorts, subjects will be randomized in a 3:1 ratio to escalating doses as follows:

- Cohort 1: 2 mg/kg KPL-404 or placebo every 2 weeks (q2wk) (n = 8)
- Cohort 2: 5 mg/kg KPL-404 or placebo q2wk (n = 8)

Cohorts 1 and 2 will start sequentially, with each escalation approved by a Safety Review Committee (SRC), which will assess in an unblinded fashion the safety, and tolerability data after all subjects complete through Week 12 and PK through Week 8 (anticipated steady state) and applicable data are available. The composition of the SRC, meeting frequency, and procedures for review and decision-making will be described in detail in the SRC Charter.

Following completion of Cohort 2, new subjects will enter Cohort 3. Subjects will be randomized in a 1:1:1 ratio to receive:

- 5 mg/kg SC every week (qwk)
- 5 mg/kg SC every 2 weeks (q2wk; weekly dosing with alternating administration of KPL 404 q2wk or placebo q2wk)
- Placebo SC qwk

To maintain the blind, all subjects will return to the study site weekly. One group (5 mg/kg SC qwk) will receive active investigational product every week at each visit. One group (Placebo SC qwk) will receive placebo every week at each visit. One group (5 mg/kg SC q2wk) will alternate between receiving active investigational product and placebo.

At approximately the end of Cohort 3 enrollment, the study will enroll subjects into Cohort 4. Subjects will be randomized in a 3:2 ratio to receive one of the following:

- KPL-404 SC q4wk (600 mg loading dose at baseline followed by maintenance dosing 400 mg q4wk at Weeks 4 and 8)
- Matched Placebo (equivalent volume) SC q4wk (loading dose at baseline followed by maintenance dose at Weeks 4 and 8)

[figure not shown]
In Cohorts 3 and 4, SRC meetings will occur on a quarterly basis while enrollment is ongoing. The initial SRC meeting in Cohort 3 will occur within approximately 90 days of the start of enrollment or once 20 subjects are enrolled, whichever occurs first. All available safety and PK data will be reviewed by the SRC at the initial meeting. Subsequent meetings will prioritize review of safety data from all active cohorts. Additional details are specified in the SRC Charter.

Subjects will be observed for at least 60 minutes following the first administration and 30 minutes after subsequent administrations. If no safety concerns are identified during that time, subjects will be discharged from the study site after all study procedures have been completed. All subjects will return to the study site at all treatment and safety follow-up visits as per the Schedule of Activities (Appendix 1) for assessments of RA parameters as well as evaluations of safety, tolerability, PK,

If a subject discontinues treatment prematurely (i.e., before the end-of-treatment visit), the subject should be encouraged to complete the procedures for the end-of-treatment visit (Week 12) within approximately 2 weeks (for Cohorts 1, 2, and 3) or 4 weeks (for Cohort 4) from last dose of study drug, as well as visits thereafter through the Week 24 visit, as per the Schedule of Activities.

At the end of the 12-week treatment period, all subjects will be followed up for safety and longevity of any treatment effect for an additional 12 weeks until the EOS visit (Week 24). An adverse event that occurs prior to study treatment administration should be recorded in the eCRF only if it is an SAE or is an AE related to a study procedure. All AEs/SAEs that occur after the first administration of study treatment through the EOS visit, whether or not they are related to the study, must be recorded in the eCRF. For subjects who terminate study participation early (i.e., before the Week 24 visit), the Investigator will report any SAEs that are reported to the Investigator within 30-day post-last dose administration.

Figure 2: Study Schema for KPL-404-C211

Abbreviations: D = day; EOS = end of study; EOT = end of treatment; PBO = placebo; qwk = every week; q2wk = every 2 weeks; SC = subcutaneous; SRC = Safety Review Committee; W = week.

NOTE: Advanced targeted therapies include bDMARDs and tsDMARDs, for example, TNF inhibitors, IL-6 receptor inhibitors, T-cell costimulatory inhibitor, anti-CD-20 antibody, and JAK inhibitors.

6.2. Number of Subjects

The study plans to enroll approximately 16 subjects in Cohorts 1 and 2, approximately 75 subjects in Cohort 3, and approximately 40 subjects in Cohort 4, across approximately 100 study sites.

6.3. Treatment Assignment

All subjects will be assigned to randomized study drug as per standard operating procedures defined by the Sponsor or designee.

In case of an emergency, the Investigator has the sole responsibility for determining if unblinding of a subject's treatment assignment is warranted. Participant safety must always be the first consideration in making such a determination. For further details on blinding, refer to Section 8.5. The date and reason that the blind was broken must be recorded.

6.4. Safety Review Committee

The SRC will consist of expert clinicians, pharmacologists, and/or statisticians. Any individual who has any affiliation with Kiniksa will be "firewalled" such that they take no part in operational activities and have no project-related communication with the study team. The SRC will review cumulative safety and PK data.

After all subjects in Cohorts 1 and 2 complete treatment through Week 12 and applicable data are available for review, an SRC meeting will be held to review unblinded safety and PK data to support dose escalation to the next cohort. Further details will be outlined in the SRC Charter.

In Cohorts 3 and 4, SRC meetings will occur on a quarterly basis while enrollment is ongoing. The initial SRC meeting in Cohort 3 will occur within approximately 90 days of the start of enrollment or once 20 subjects are enrolled, whichever occurs first. All available safety and PK data will be reviewed by the SRC at the initial meeting. Subsequent meetings will prioritize review of safety data from all active cohorts. Additional details are specified in the SRC Charter, and the charter may be amended as necessary for the SRC to review safety and PK data.

In the event of any concern regarding subject safety or risk mitigation, the SRC may contact the Sponsor Head of Global Medical Safety for additional discussion in order to finalize the decision. However, the Sponsor Head of Global Medical Safety will not be given access to subject-level unblinded data. Details of the review process will be defined in the SRC Charter.

6.5. Stopping Rules

A subject may be discontinued from treatment due to any Grade 3 (severe) or any Grade 4 (life-threatening) TEAE, regardless of causality.

For the study, enrollment in a cohort will be paused for review under any of the circumstances below:

- Two subjects develop the same Grade 3 TEAE
- One subject has a Grade 4 (life-threatening) or Grade 5 (fatal) TEAE

Any such review will be conducted by the SRC in conjunction with the Sponsor Head of Global Medical Safety and supported by additional clinical experts as appropriate. At the conclusion of the review, the study will resume (or otherwise) upon the approval of the Sponsor Head of Global Medical Safety.

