6.6. Study Termination or Temporary Suspension

The Sponsor reserves the right to temporarily suspend or terminate this study, in part or whole, at any time. The reasons for temporarily suspending or terminating the study may include but are not limited to:

- The incidence or severity of AEs in this or other studies indicates a potential health hazard to subjects
- Subject enrollment is unsatisfactory
- Noncompliance that might significantly jeopardize the validity or integrity of the study
- Recommendation to suspend or terminate the study by independent body such as a health authority
- Sponsor decision to terminate the study

Where required by applicable regulations, the Investigator or head of the medical institution must inform the Institutional Review Board (IRB)/International Ethics Committee (IEC) promptly and provide the reason(s) for the suspension/termination. If the study is suspended for safety reasons and it is deemed appropriate by the Sponsor to resume the study, approval from the relevant regulatory authorities (and IECs when applicable) will be obtained prior to resuming the study.

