7.3. Treatment Discontinuation, Withdrawal of Consent, and Lost to Follow-Up Criteria

Subjects are free to discontinue study treatment or withdraw consent from the study at any time, without prejudice to their medical care.

Treatment Discontinuation

Subjects will be discontinued from study treatment if any of the following criteria are met.

- Change in compliance with any inclusion/exclusion criterion that is clinically relevant and affects subject safety as determined by the Investigator
- Noncompliance with the study restrictions that might affect subject safety or study assessments/objectives, as considered applicable by the Investigator
- Pregnancy
- Thromboembolic event
- Anaphylactic reaction related to investigational medicinal product (IMP)
- Severe infection (severe AE or SAE) or opportunistic infections (regardless of severity/seriousness)
- Any clinically relevant sign or symptom, including a RA flare requiring prohibited study medications(s), that in the opinion of the Investigator warrants subject discontinuation from study treatment.

Upon decision to discontinue treatment, the Sponsor should be notified immediately. If a subject is prematurely discontinued from IP (study treatment), he or she should complete the end of treatment (EOT) visit (Week 12) within approximately 2 weeks (for Cohorts 1, 2, and 3) or 4 weeks (for Cohort 4) from last dose of study drug, as well as visits thereafter through Week 24, as per the Schedule of Activities, for all safety and efficacy assessments. The Investigator may also request that the subject return for additional visits.

Withdrawal of Consent

Subjects are free to withdraw consent from the study at any time, without prejudice to their medical care. Only study subjects who withdraw consent will be considered discontinued from the study (as differentiated from treatment discontinuation).

If a subject is discontinued from the study (withdraws consent), the Sponsor will be notified, and the date and reasons for the study discontinuation / withdrawal of consent will be documented in the subject's electronic case report form (eCRF).

Lost to Follow-Up

Subjects will be defined as lost to follow-up if they have not responded to 3 phone calls and 1 registered post letter. Missing data due to lost to follow-up will be covered in the Statistical Analysis Plan (SAP).

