8.2.1. COVID Vaccines

Subjects are required to have completed a COVID-19 vaccine regimen to be eligible for the study. Subjects who desire to receive any additional COVID vaccines during study must discontinue treatment and wait at least 4 months after last dose of study drug to receive the vaccine in order for KPL-404 to wash out completely.

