9.5. Administration

KPL-404 drug product and placebo will be administered by SC injection. There is no restriction on fasting, water intake, or postures pre-/post-dose. Additional details on administration can be found in the Pharmacy Manual.

Investigational product should be administered at a study visit scheduled within the protocol-specified time window. If the study visit occurs outside the protocol-specified time window, every effort should be made to complete the visit procedure, including assessments, sample collection, and investigational product administration, as close as possible to the protocol-specified study visit time interval. Provided that sequential administration of investigational product doses can be separated by at least 24 hours, study visits occurring outside the protocol-specified time window should include administration of investigational product. While an out-of-window administration of investigational product would be a protocol deviation, it is preferable to have the out-of-window administration rather than to have a missed dose.

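### The stopping rule in Protocol 6.5 pauses enrollment but names no hold on dosing, and scheduled SRC review is tied to enrollment being open

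*Protocol*

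**What the plan says.** **Protocol 6.5** is the study's stopping rule. On either trigger, "enrollment in a cohort will be paused for review under any of the circumstances below". The triggers are two subjects with the same Grade 3 TEAE, or one subject with a Grade 4 or Grade 5 TEAE; neither depends on causality. The SRC reviews together with the Sponsor Head of Global Medical Safety, and at the end "the study will resume (or otherwise) upon the approval of the Sponsor Head of Global Medical Safety". The section's only statement about dosing is that an individual subject may be taken off treatment for that subject's own Grade 3 or 4 event.

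**Protocol 6.4** sets the meeting calendar: "In Cohorts 3 and 4, SRC meetings will occur on a quarterly basis while enrollment is ongoing". After the first Cohort 3 meeting, these meetings give priority to safety data from all active cohorts. Details are left to the SRC Charter.

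**Protocol 6.6** gives a general power: "The Sponsor reserves the right to temporarily suspend or terminate this study, in part or whole, at any time". After a suspension for safety reasons, "approval from the relevant regulatory authorities (and IECs when applicable) will be obtained prior to resuming the study". **Protocol 7.3** works subject by subject: "Subjects will be discontinued from study treatment if any of the following criteria are met", a list that includes thromboembolic events, related anaphylaxis, and severe or opportunistic infection.

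**The concern.** The review asks whether it is safe to go on giving KPL-404, but the automatic action falls on enrollment. Subjects already randomized are the ones exposed, and nothing in 6.5 says whether their next injection waits for the review. Sites could read the rule differently on the day of a fatal event, because the closing sentence speaks of the study resuming while the opening sentence stops only enrollment.

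A dose given during the review cannot be withdrawn. In the context of vaccination, 8.2.1 tells subjects to "wait at least 4 months after last dose of study drug to receive the vaccine in order for KPL-404 to wash out completely". A short hold would not lower exposure already reached. Its benefit is that no further injection is given before the SRC has looked.

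Once a cohort is full there is no enrollment left to pause, yet dosing continues for weeks. In Cohort 4, the last to enroll, the calendar of SRC meetings also lapses when enrollment closes.

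**Working it through.** There is no sample size, power or alpha figure to reproduce. The check is a comparison of the text, a count of doses, and an illustration of scale.

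**1. Does any supplied section hold dosing at study or cohort level after a 6.5 trigger?**

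| Section | Action | Applies to | Automatic on a 6.5 trigger? |
|---|---|---|---|
| 6.5 | Pause enrollment, then SRC review | A cohort | Yes |
| 6.5 | May discontinue treatment | The affected subject | No, optional |
| 6.6 | Suspend or terminate | Study, in part or whole | No, sponsor discretion |
| 7.3 | Discontinue treatment | The individual subject | Only for the listed events |
| Appendix 1 | Withhold dosing on a positive urine pregnancy test | The individual subject | Not related |

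No row holds dosing in the cohort.

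**2. Doses left for the last subject when a cohort fills** (dosing weeks from Protocol Appendix 1; maximum doses from SAP 4.5). Planned doses minus the Day 1 dose:

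- Cohort 3, Weeks 0 to 11: 12 − 1 = 11 of 12.
- Cohort 4, Weeks 0, 4 and 8: 3 − 1 = 2 of 3.

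This needs no accrual assumption. An enrollment pause stops none of these doses.

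**3. Dosing without a scheduled SRC meeting**

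- Cohort 4: from the last subject's Day 1 to that subject's Week 8 dose is 8 weeks. This is shorter than a quarter (about 13 weeks), so at most one quarterly meeting is lost.
- Cohort 3: Cohort 4 starts enrolling at about the end of Cohort 3 enrollment (6.1). Quarterly meetings then continue and cover all active cohorts, so Cohort 3's 11-week tail is largely covered.

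**4. Illustration of scale.** Assume even accrual over T weeks and no dropout, with q2wk active doses at even weeks 0 to 10. T is not in the documents, except that 15.6 weeks for Cohort 4 comes from dates. Last entry is 31 March 2024 (end of the estimated completion quarter) minus 168 days, or 15 October 2023, which is 109 days after the protocol date of 28 June 2023; 109/7 = 15.6.

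Active doses due to already enrolled subjects in any 7 days of steady accrual:

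- Cohort 3: (25 × 11 + 25 × 5)/T = 400/T.
- Cohort 4: 24 × 2/T = 48/T.

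Share of scheduled injections that fall after enrollment closes:

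- Cohort 3: (0 + 1 + … + 11)/(12T) = 5.5/T.
- Cohort 4: (0 + 4 + 8)/(3T) = 4/T.

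| Cohort | T (weeks) | Active doses per 7 days | Share after closure |
|---|---|---|---|
| 3 | 26 | 15.4 | 21% |
| 3 | 39 | 10.3 | 14% |
| 3 | 52 | 7.7 | 11% |
| 4 | 15.6 | 3.1 | 26% |
| 4 | 26 | 1.8 | 15% |

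**5. Cost of a 7-day hold.** A Cohort 3 subject has one injection due in 7 days, so usually at most 1 of 12 is delayed or missed. An already enrolled Cohort 4 subject has 2 further doses over 12 weeks, so about 2/12 = 17% have one due in any 7 days.

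**The case against.** The strongest reply is that 6.5 is a sensitive trigger paired with a mild action, and that the heavier tools lie elsewhere. One event is enough, whatever its cause, so stopping all dosing each time would be disproportionate. The sponsor can suspend at any time under 6.6, 7.3 removes subjects with the most worrying events, SAEs reach the sponsor within 24 hours (10.10), and the Charter may provide for a hold or for ad hoc meetings. The words "the study will resume (or otherwise) upon the approval of the Sponsor Head of Global Medical Safety" can also be read as implying a wider stop.

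Much of this stands. It is why the fix limits the dosing hold to related Grade 4 or 5 events and leaves the other triggers alone. But 6.6 is discretionary and not tied to these triggers, 7.3 protects only the subject who has had the event, and an implied wider stop is not an instruction that a site can follow.

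A reader might go further in four directions that the documents do not support:

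- **That 9.5 directs sites to keep dosing through a safety review**, because "it is preferable to have the out-of-window administration rather than to have a missed dose". That section concerns visit windows. It says nothing about safety holds and should carry no weight here.
- **That the whole rule is void in a full cohort.** Only the pause is empty; the trigger still reads as calling for SRC review.
- **That Cohort 3 goes unreviewed after it fills.** Meetings during Cohort 4 enrollment largely cover it. Whether an event in a full Cohort 3 pauses Cohort 4 enrollment is unclear, but neither reading stops dosing in Cohort 3.
- **That the trial has no dosing hold at all.** The Charter was not supplied, so only the protocol's silence is shown.

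The dose counts also do not measure harm: the documents give no event rate, and accrual is assumed.

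**Conclusion.** The point holds as a gap in the protocol's safety rule. A sponsor following 6.5 to the letter would go on dosing enrolled subjects while a Grade 4 or 5 event is reviewed, and in a full cohort the pause would do nothing. This is more than missing detail, because the stated action addresses enrollment when the risk lies in further dosing.

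The firm sizes come from the schedule: up to 11 of 12 doses (Cohort 3) or 2 of 3 (Cohort 4) outstanding for the last subject, and up to 8 weeks of Cohort 4 dosing without a scheduled SRC meeting. The figures that depend on T are illustrations only. The conclusion assumes that the Charter does not already supply a hold; if it does, the remaining task is to put it where sites will see it. The change is worth making, but the existing backstops mean that subjects are not left wholly unprotected.

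**What to change.** 1. **In 6.5 and 6.4**, state that the triggers and the SRC review apply until the last subject's last dose, whether or not enrollment is open, and continue scheduled SRC review to that point.
2. **In 6.5**, for a Grade 4 or 5 TEAE assessed as possibly or definitely related (categories in 10.7), hold further dosing in the affected cohort until an expedited SRC review clears it. About 7 days is a reasonable target, to be aligned with the Charter; 24-hour SAE reporting helps but does not by itself show that 7 days is achievable. Keep the enrollment-only pause for the other triggers, and allow a delayed dose to be given once cleared.

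**Cost.** Protocol wording, Charter alignment, about one extra SRC meeting, and usually at most one delayed or missed weekly dose per subject. SAP 1.4 already treats a missed dose followed by resumption before Week 12 as an interruption, so a short hold needs no new estimand rule. Allowing the delayed dose matters for a subject whose last planned injection falls in the hold.

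**Downsides.** A related event in a placebo subject would also trigger the hold until the SRC has reviewed it unblinded. A longer hold could dilute the Week 12 effect. If it became a safety suspension under 6.6, it would need that section's approvals before resuming.
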